4.7.6.6 CCI

The CCI will be presented by treatment group.

It will be computed with the following formula:

$$\text{CCI} = \frac{(\text{follow-up time [days]} - \text{sum of durations of CCI})}{\text{follow-up time (years)}}$$

Follow-up time will be computed as detailed in Section 4.1.7.

For CCI with a resolution date after the treatment completion/discontinuation, the number of days of duration after the treatment completion/discontinuation, i.e. out of the follow-up period, will be subtracted from the sum of durations of CCI.

Non-parametric ANCOVA model with a randomisation-based methodology as proposed by Koch et al [4] will be used to analyse the ratio of the means between colistimethate sodium and placebo adjusting for any covariates effect and test the null hypothesis of the ratio of means equal to 1. Considering the sample size foreseen for this analysis, there won't be any correction for type I error. A LOGRATIO conversion will be applied.

The model will include treatment group, pooled site, i.e. country, as detailed in Section 4.9.1, and use of stable concomitant therapy with oral macrolides as covariates. No stratification variable will be included.

Treatment effect coefficient will be presented along with standard error, associated test statistic and two-sided p-value. A two-sided p-value of <0.05 will be considered statistically significant.

Treatment effect coefficient and associated 95% CI will be exponentiated to obtain estimates and 95% CI for the ratio of the means.

Due to the fact that the p-value computation is based on the re-randomisation of the population, while the CI is based on repeated random sampling theory, there might be disagreement regarding the treatment effect using these two different approaches. Even if these occurrences are quite infrequent, it's worth stating that the p-value from the randomisation test is based on a more realistic and minimal assumptions and should take precedence [5].

CONFIDENTIAL

Sponsor:	Zambon S.p.A.	Protocol Number:	Z7224L01
----------	---------------	------------------	----------

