  MODEL count = treatment_d psite_d1-psite_dx med_d / OFFSET=log_years
  DIST=NEGBIN;
  /* >1000 imputations since some will be discarded due to convergence issues with the
  model */
  BAYES NBI=1000 NMC=11000 THIN=10 OUTPOST=dataset2 SEED=34783129;
RUN;

DATA dataset3;
  SET dataset2;
  RENAME treatment_d =c_treatment_d
  psite_d1-psite_dx=c_psite_d1-c_psite_dx
  med_d=c_med_d;
RUN;
```

CONFIDENTIAL

Sponsor:	Zambon S.p.A.	Protocol Number:	Z7224L01
----------	---------------	------------------	----------

```

PROC SQL;
  CREATE TABLE dataset4 AS
  SELECT dataset1.*, dataset3.*
  FROM dataset1, dataset3
  ORDER BY Iteration;
QUIT;

DATA dataset5;
  SET dataset4;
  BY Iteration;
  ARRAY c[*] c_psite_d1-c_psite_dx c_med_d;
  ARRAY x[*] psite_d1-psite_dx med_d;
  k=1/Dispersion;
  imp_subj=(years<365/365.25);
  years_imp=MAX(years,365/365.25);
  log_years_imp=LOG(years_imp);
  linpred_1=.;
  IF imp_subj THEN DO;
    years_miss=years_imp-years;
    linpred_1=Intercept;
    DO i=1 TO DIM(c);
      linpred_1+c[i]*x[i];
    END;
    linpred_mar=linpred_1+c_treatment_d*treatment_d;
    linpred_cr=linpred_1+c_treatment_d;
    y1hat_mar=years*EXP(linpred_mar);
    y2hat_mar=years_miss*EXP(linpred_mar);
    y1hat_cr=years*EXP(linpred_cr);
    y2hat_cr=years_miss*EXP(linpred_cr);
    CALL STREAMINIT(3231212);
    y2_mar=RAND('NEGBINOMIAL',(1+y1hat_mar)/(1+y1hat_mar+y2hat_mar),k+count);
    y2_cr=RAND('NEGBINOMIAL',(1+y1hat_cr)/(1+y1hat_cr+y2hat_cr),k+count);
    y_imp_mar=count+y2_mar;
    y_imp_cr=count+y2_cr;
  END;
  ELSE DO;
    y_imp_mar=count;
    y_imp_cr=count;
  END;
RUN;

```

Notes:

- dataset1 includes one record per patient;
- count represents the total number of exacerbations observed for each patient;
- treatment represents the treatment group (treatment order: 1 = colistimethate sodium, 2 = placebo);

CONFIDENTIAL

Sponsor:	Zambon S.p.A.	Protocol Number:	Z7224L01
----------	---------------	------------------	----------

- treatment_d represent the dummy variables for treatment group (values of the dummy variables: 0 for colistimethate sodium; 1 for placebo);
- Psite represents the pooled site, i.e. country, as detailed in [Section 4.9.1](#);
- psite d1-psite_dx represent the dummy variables for the (pooled) site;
- Med represents use of stable concomitant therapy with oral macrolides (e.g. azithromycin or erythromycin or clarithromycin) (Yes/No);
- med_d represents the dummy variable for use of stable concomitant therapy with oral macrolides;

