- years represents the follow-up time in years;
- log_years represents the logarithm of the follow-up time in years.

Analysis step

The imputed dataset obtained using the above SAS code will be finally analysed and the results will be combined.

```
ODS OUTPUT LSMeans=lsmeans1 Estimates=ratios1;
PROC GENMOD DATA=dataset5;
  BY Iteration;
  CLASS treatment psite med;
  /* MAR imputation */
  MODEL y_imp_mar = treatment psite med / OFFSET=log_years_imp DIST=NEGBIN;
  /* Alternative MODEL statement: copy reference imputation */
  MODEL y_imp_cr = treatment psite med / OFFSET=log_years_imp DIST=NEGBIN;
  LSMEANS treatment / ilink cl diff exp om;
  ESTIMATE 'Col. Sodium / Placebo' treatment 1 -1 / exp;
RUN;
```

```
DATA lsmeans2;
  SET lsmeans1 (WHERE=(zValue ne .));
  BY Iteration;
  IF first.Iteration THEN _Imputation_+1;
  IF _Imputation_ LE 1000;
RUN;
```

```
ODS OUTPUT ParameterEstimates=lsmeans3;
PROC MIANALYZE PARMS=lsmeans2;
  CLASS treatment;
  MODELEFFECTS treatment;
RUN;
```

```
DATA lsmeans4;
  SET lsmeans3;
  exp_est=EXP(Estimate);
  exp_lcl=EXP(LCLMean);
  exp_ucl=EXP(UCLMean);
RUN;
```

CONFIDENTIAL

Sponsor:	Zambon S.p.A.	Protocol Number:	Z7224L01
----------	---------------	------------------	----------

```
DATA ratios2 (RENAME=LBetaEstimate=Estimate);
  SET ratios1 (WHERE=(ChiSq ne .));
  BY Iteration;
  IF first.Iteration THEN _Imputation_+1;
  IF _Imputation_ LE 1000;
  Effect='Label';
RUN;
```

```
ODS OUTPUT ParameterEstimates=ratios3;
PROC MIANALYZE PARMS =ratios2;
  CLASS Label;
  MODELEFFECTS Label;
RUN;
```

```
DATA ratios4;
  SET ratios3;
  exp_est=EXP(Estimate);
  exp_lcl= EXP (LCLMean);
  exp_ucl= EXP (UCLMean);
RUN;
```

- **Tables that require Non-Parametric Randomization-Based Analysis of Covariance.**

The macro NParCov4, reported in [Appendix 4](#), will be applied with the following parameters.

For the analysis of pulmonary exacerbation score:

```
%NPARCOV4 ( outcomes = outcome,
             covars = psite med,
             trtgrps = treatment,
             strata = NONE,

             hypoth = NULL /*for p-value*/,
             hypoth = ALT /*for CI*/,

             transform = NONE,

             dsnin = dataset,
             dsnout = outdat,
             exact = %str(NO)
           );
```

For the analysis of annualised number of pulmonary CCI:

```
%NPARCOV4 ( outcomes = outcome,
             covars = psite med,
             trtgrps = treatment,
             strata = NONE,
```

CONFIDENTIAL

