Sponsor:	Zambon S.p.A.	Protocol Number:	Z7224L01
----------	---------------	------------------	----------

```
hypoth = NULL /*for p-value*/,  
hypoth = ALT /*for CI*/,  
  
transform = LOGRATIO,  
  
    dsnin = dataset,  
    dsnout = outdat,  
    exact = %str(NO)  
);
```

Notes:

- dataset includes one record per patient;
- outcome represents the outcome observed for each patient, ie the pulmonary exacerbation score or the annualised number of pulmonary CCI
- treatment represents the treatment group (treatment order: 1 = colistimethate sodium, 0 = placebo);
- Psite represents the pooled site, i.e. country, as detailed in [Section 4.9.1](#);
- Med represents use of stable concomitant therapy with oral macrolides (e.g. azithromycin or erythromycin or clarithromycin) (Yes/No);

CONFIDENTIAL

Sponsor:	Zambon S.p.A.	Protocol Number:	Z7224L01
----------	---------------	------------------	----------

5 Tables and Listings

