Appendix 4: Macro Code for non-parametric ANCOVA

The non-parametric ANCOVA models will be fitted using the randomisation-based methodology as proposed by Koch et al ^[4] applying the macro written by Zink and Koch, reported below.

NParCov4
Non-Parametric Randomisation-Based Analysis of Covariance

PPD
JMP Life Sciences
SAS Institute, Inc.

and

PPD
Biometric Consulting Laboratory
Department of Biostatistics
University of North Carolina at Chapel Hill

Copyright 2001 - 2017

Inputs:

outcomes List of outcome variables. Numeric. At least 1 required. Need to be (0,1)
outcomes for LOGISTIC, PODDS, LOGRANK, WILCOXON

covars List of covariates. Numeric

exposures Numeric exposure variables for (0,1) outcome for WILCOXON, LOGRANK and INCSENS.
Need same number of variables as OUTCOMES.

strata Variable that defines strata. Numeric. NONE (default) for no stratification (i.e. a single stratum)

trtgrps Defines the treatments. Numeric. Differences defined are higher number (trt2) - lower number (trt1). 2 treatments required.

hypoth NULL (default), ALT. NULL groups treatments for estimating variance. ALT estimates variance within treatment

transform NONE, LOGISTIC, PODDS, LOGRANK, LOGRATIO, WILCOXON, INCSENS. Default is NONE.

combine NONE, LAST, FIRST, PRETRANSFORM. Only usable when strata is not NONE Default is NONE.

c Used in calculation of strata weights. $0 <= c <= 1$. 0 assigns equal weights to strata, 1 is for Mantel-Haenssel weights. Default is 1.

alpha For CI (0.05 default)

seed Seed for exact p-values and confidence intervals. (Default 0)

nreps Number of random data sets to generate. (Default 1000)

exact NO (Default), YES. Must be NO for TRANSFORM = PODDS. Only available for a single outcome. Under hypoth = ALT performs sampling with replacement within treatment (bootstrap). Under hypoth = NULL performs sampling without replacement, essentially shuffling

CONFIDENTIAL

Sponsor:	Zambon S.p.A.	Protocol Number:	Z7224L01
----------	---------------	------------------	----------

```

treatment codes among observations (permutation).

symsize      Define space requirements for IML (Default 20000)

dsnin        Input Data (required)

dsnout       Output data (required)

details      YES (default), NO.Print analysis details to the log.

*****
*****
*****
*****
*****;

%macro NPARCOV4( outcomes = ,
                covars = ,
                strata = %str(NONE),
                trtgrps = ,
                hypoth = %str(NULL),

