    %if ^%length(%exposures) %then %do;
        %put ERROR: EXPOSURES should be specified for WILCOXON LOGRANK INCDENS;
        %goto stopmac;
    %send;
%send;

%if ^%index(LOGISTIC PODDS LOGRATIO INCDENS, %upcase(%transform)) and %upcase(%combine) =
PRETRANSFORM %then %do;
    %put ERROR: COMBINE = PRETRANSFORM only available for LOGRATIO LOGISTIC PODDS INCDENS;
    %goto stopmac;
%send;

%if %upcase(%strata) ne NONE and %upcase(%combine) = NONE %then %do;
    %put ERROR: STRATA specified but COMBINE = NONE;
    %goto stopmac;
%send;

%if ^%index(NO YES, %upcase(%exact)) %then %do;
    %put ERROR: EXACT must be one of NO YES;
    %goto stopmac;
%send;

%if %upcase(%transform) = PODDS and %upcase(%exact) = YES %then %do;
    %put ERROR: PODDS must have EXACT = NO;
    %goto stopmac;
%send;

*****;
*****;
*****;

ods noresults;

data _null_;
    call symput("numresp", left(countw(compbl("%outcomes"), " ")));
    call symput("numcov", left(countw(compbl("%covars"), " ")));
    %if %index(LOGRANK WILCOXON INCDENS, %upcase(%transform)) %then %do;
        call symput("numtime", left(countw(compbl("%exposures"), " ")));
    %send;
    call symput("numstratwrd", left(countw(compbl("%strata"), " ")));

```

CONFIDENTIAL

Sponsor:	Zambon S.p.A.	Protocol Number:	Z7224L01
----------	---------------	------------------	----------

```

run;

%if %upcase(%sexact) = YES and %numresp > 1 %then %do;
  %put ERROR: OUTCOMES can only have one variable for EXACT = YES;
  %goto stopmac;
%end;

%if %ysevalf(%numstratwrd ne 1) %then %do;
  %put ERROR: STRATA can only have a single variable specified;
  %goto stopmac;
%end;

%if %index(LOGRANK WILCOXON INCDENS, %upcase(%stransform)) %then %do;
  %if %numtime ne %numresp %then %do;
    %put ERROR: EXPOSURES and RESPONSE must have same number of variables specified for
WILCOXON LOGRANK INCDENS;
    %goto stopmac;
  %end;
%end;

%if %index(LOGRANK WILCOXON, %upcase(%stransform)) %then %do;
  %let workoutcomes = ;
  %do i = 1 %to %numresp;
    %let tempoutcomes = %transform._%scan(%outcomes, %i);
    %let workoutcomes = %workoutcomes %tempoutcomes;
  %end;
%end;
%else %if %index(INCDENS, %upcase(%stransform)) %then %do;
  %let workoutcomes = ;
  %do i = 1 %to %numresp;
    %let tempoutcomes = INC_%scan(%outcomes, %i);
    %let workoutcomes = %workoutcomes %tempoutcomes;
  %end;
%end;
%else %do;
  %let workoutcomes = %outcomes;
%end;

data _work_temp;
  set %dsnin end = eof;

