%send;

*****;
*****;
*****;

proc iml symsize = %symsize;
  start NEARCOV4(h, r, t, c, hypoth, f, V, n, varnames, combine, transform);
    wh = CREATEWH(h, c, n);
    if t>0 then X = I(r)//J(t,r,0);
    else if t=0 then X = I(r);

    if transform = 'LOGISTIC' & combine = 'PRETRANSFORM' then run TRANSFIRST(h, r, t, n,
    f, wh, V, X, hypoth, varnames, 0, 0, 'LOGISTIC');
    else if transform = 'PODDS' & combine = 'PRETRANSFORM' then run PROTRANSFIRST(h, r,
    t, n, f, wh, V, X, hypoth, varnames);
    else if transform = 'LOGRATIO' & combine = 'PRETRANSFORM' then run TRANSFIRST(h, r,
    t, n, f, wh, V, X, hypoth, varnames, 0, 0, 'LOGRATIO');
    else if transform = 'INCDENS' & combine = 'PRETRANSFORM' then run TRANSFIRST(h, r, t,
    n, f, wh, V, X, hypoth, varnames, 0, 0, 'INCDENS');
    else do;
      if (transform = 'LOGISTIC' | transform = 'PODDS') & combine ^= 'PRETRANSFORM' then
run TRANSFORM(h, r, t, f, V, hypoth, n, 'LOGISTIC');
      else if (transform = 'LOGRATIO') & combine ^= 'PRETRANSFORM' then run TRANSFORM(h,
r, t, f, V, hypoth, n, 'LOGRATIO');
      else if (transform = 'INCDENS') & combine ^= 'PRETRANSFORM' then run TRANSFORM(h,
r, t, f, V, hypoth, n, 'INCDENS');

      Vdh = VARSTRAT(h, r, t, V, n);
      dh = CREATEDH(h, r, t, f);

      if transform = 'LOGRANK' & (combine = 'LAST' | combine = 'NONE') then run LAST(n,
h, r, t, dh, wh, Vdh, X, hypoth, varnames, 0, 0, 0);
      else if transform = 'LOGRANK' & combine = 'FIRST' then run FIRST(h, r, t, dh, wh,
Vdh, X, hypoth, varnames, 0, 0, 0);
      else if transform = 'WILCOXON' & (combine = 'LAST' | combine = 'NONE') then run
LAST(n, h, r, t, dh, wh, Vdh, X, hypoth, varnames, 0, 0, 0);
      else if transform = 'WILCOXON' & combine = 'FIRST' then run FIRST(h, r, t, dh, wh,
Vdh, X, hypoth, varnames, 0, 0, 0);
      else if transform = 'LOGISTIC' & (combine = 'LAST' | combine = 'NONE') then run
LAST(n, h, r, t, dh, wh, Vdh, X, hypoth, varnames, 0, 0, 1);
      else if transform = 'LOGISTIC' & combine = 'FIRST' then run FIRST(h, r, t, dh, wh,
Vdh, X, hypoth, varnames, 0, 0, 1);
      else if transform = 'LOGRATIO' & (combine = 'LAST' | combine = 'NONE') then run
LAST(n, h, r, t, dh, wh, Vdh, X, hypoth, varnames, 0, 0, 1);
      else if transform = 'LOGRATIO' & combine = 'FIRST' then run FIRST(h, r, t, dh, wh,
Vdh, X, hypoth, varnames, 0, 0, 1);
      else if transform = 'PODDS' & combine = 'FIRST' then run PROFIRST(h, r, t, dh, wh,
Vdh, X, hypoth, varnames);

```

CONFIDENTIAL

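### As coded, the non-parametric ANCOVA adjusts for a single country number, so one secondary result depends on how the countries happen to be numbered

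*SAP*

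**What the plan says.** For the secondary endpoint in SAP 4.7.6.6 the text reads "The model will include treatment group, pooled site, i.e. country, as detailed in" section 4.9.1, together with macrolide use, and no stratification variable. SAP 4.7.4.8 says the same for the ordered exacerbation score, and SAP 4.9 confirms that both analyses share these covariates.

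SAP 4.14 states that the macro NParCov4 will be applied with listed parameters. Both calls give "covars = psite med" and set the strata to none. The notes add: "Psite represents the pooled site, i.e. country, as detailed in" section 4.9.1. No numeric codes for countries are given.

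SAP Appendix 4 describes the covariate input as "List of covariates. Numeric".

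Elsewhere in SAP 4.14 country is categorical. The GLM, PHREG, GENMOD and MIXED code lists psite in a CLASS statement. The imputation code, where no CLASS statement is used, has separate variables and says so: "psite d1-psite_dx represent the dummy variables for the (pooled) site".

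**The concern.** A country code is a label. Used as a number, it makes the model treat country 10 as lying nine steps beyond country 1 on a linear scale, which has no meaning. Another programmer with another code list would get a different estimate and p-value from the same data, and both would comply with the plan.

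The 4.7.6.6 endpoint is tested at two-sided 0.05, and the SAP gives this method's p-value precedence over its confidence interval. SAP 4.7.5 puts the secondary endpoints in a fixed sequence in which a failed test blocks all later ones. An arbitrary code could therefore influence more than one conclusion.

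**Working it through.** The plan states no figure on this point, so there is none to reproduce. The check traces the code and then sizes the effect.

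**Trace through Appendix 4.**
- The macro counts covariates as the words in the list: psite and med, so t = 2.
- It takes raw means (PROC MEANS) and covariances (PROC CORR) of those two variables.
- The design matrix is set by "if t>0 then X = I(r)//J(t,r,0"), one row per listed covariate. Nothing expands levels.
- A character country variable would not run. A numeric code runs without warning, because the input checks never look at covariate levels.

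**Algebra.** Let d be the vector of arm differences (outcome, covariates) and V its covariance matrix. With X = (1, 0, 0)', the macro's estimate (X'V⁻¹X)⁻¹X'V⁻¹d reduces to

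β = d_y − V_yx V_xx⁻¹ d_x.

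Replacing the code by a + b·code leaves β unchanged, so reversing the order does nothing. A general renumbering is not linear, so it changes both V_yx and d_x. A full set of k − 1 indicators spans the same space whichever country is the reference, so β is then free of labels.

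**Numerical confirmation.** The estimator was re-implemented and applied to simulated trials.
- Inputs from SAP 3.9: 377 subjects, placebo rate 1.2701, dispersion 0.273, and rate ratio 0.8256/1.2701 = 0.65. From SAP 3.1: 15 countries, the stated maximum.
- Assumed: between-country SD of the log rate, uneven country sizes, 25% macrolide use, 20% early dropout, blocks of 4, and an alternative rate ratio of 0.75.

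Ordered score, one trial:

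| Country coding | β | p |
|---|---|---|
| Original code | −0.1235 | 0.1504 |
| Reversed code | −0.1235 | 0.1504 |
| Random renumbering | −0.1216 | 0.1584 |
| Indicators, either reference country | −0.1232 | 0.145 |

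Log ratio of means (the 4.7.6.6 scale), one trial: over 300 renumberings p ran from 0.136 to 0.186; indicators gave 0.134.

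**How often it changes the conclusion.** On the log-ratio scale (mean exacerbation duration assumed to be 16 days), one arbitrary numbering was compared with indicators. The entries are the share of trials in which the two disagree at 0.05:

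| Country SD (log rate) | Rate ratio 0.65 | Rate ratio 0.75 |
|---|---|---|
| 0.2 | 2.5% | 4.5% |
| 0.4 | 4.7% | 7.1% |
| 0.6 | 6.5% | 12.3% |

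Average power loss was 0.4 to 3 points, except 8 points at rate ratio 0.75 with SD 0.6. At SD 0.4 the standard error is about 5% larger than with indicators.

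A different quantity is whether any of 200 renumberings moves p across 0.05. For the ordered score this happened in 1, 6, 7 and 8 of 60 trials in four settings (SD 0.3 or 0.6, rate ratio 0.65 or 0.75), which is about 2% to 13%. In one such trial p ran from 0.024 to 0.129, against 0.045 with indicators.

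**Type I error.** Over 2000 null trials for the ordered score, rejection was 4.6% with the single code and 5.7% with indicators. The simulation standard error is √(0.05 × 0.95/2000) = 0.49 points, so both lie within 1.5 standard errors of 5%.

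**The case against.** The strongest reply is that the call is schematic. It lists the null and the alternative setting of the hypothesis parameter in one invocation, although these must be two runs, and it uses placeholder names. The text promises country as a covariate and never says it is scored linearly. The same authors built indicators in the imputation code, so the program actually run may have passed indicators here too. That possibility stands: the documents do not show what was executed. It does not remove the fault in the plan. The parameters are stated as those to be applied, psite is defined as country, indicators have their own names where they are meant, and the opening caveat about example code in SAP 4.14 covers only descriptive statistics and frequency counts.

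The second reply is that the harm is limited, and most of this stands. Randomisation is blocked within site and macrolide use (SAP 3.7), so covariate adjustment serves precision. The ordered-score analysis is labelled a further investigation. The 4.7.6.6 endpoint also has a supportive ANCOVA whose code treats country as a CLASS effect. That analysis is a useful check, but it estimates a difference in means and is not the main test.

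**Conclusion.** The point holds for the plan as written. The code contradicts the covariate adjustment that the text describes, and the result depends on an unspecified choice. That dependence follows from the algebra and needs no assumption. Its size does: roughly 2% to 12% disagreement on significance, over assumed country SDs of 0.2 to 0.6 and rate ratios of 0.65 and 0.75. The realised number of countries and the between-country variation are not in the documents.

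A reader might infer more than this, in four ways that the documents do not support:
- **A biased or anti-conservative test.** Blocking within site and the simulated rejection rates speak against it.
- **A threat to the primary result.** The primary negative binomial model declares country in CLASS.
- **A worst case over many renumberings as the risk in this trial.** The trial uses one numbering, so the comparison of a single numbering with indicators is the relevant one.
- **A known effect on later secondary tests.** The order in SAP 4.7.5 is redacted, so the position of this endpoint and any knock-on effect cannot be seen.

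The point should be corrected, but it does not undermine the trial's main conclusion.

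**What to change.** First establish what the executed program passed as psite. If it was a single code:
- In both macro calls, replace psite with k − 1 country indicators coded 0/1 and keep the macrolide indicator, also coded 0/1.
- Group small countries by a stated rule that does not use outcomes. SAP Addendum section 6.1 reports countries with very few subjects, and section 6.1.3 names three without a calculable rate ratio for lack of treated subjects. The grouped-country variable from the March 2022 Note to File could serve, provided its rule is written down.
- Rerun Tables 14.2.1.5 and 14.2.2.8.1 and label them post hoc, as SAP section 1 requires for changes after unblinding. The Note to File's reruns do not include these two tables.

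The cost is a little programming and more covariates in the macro: at most 14 country indicators plus one for macrolides, 15 in place of 2, and fewer with grouping.

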5.1 Table Format

All output will be produced using SAS version 9.4 or a later version.

- All TFLs will be produced in landscape format on *American letter size / A4 paper size*, unless otherwise specified. <Check with Medical Writer the CSR paper size so both documents are consistent>
- All TFLs will be produced using the Courier New font, size 8, which is the smallest acceptable point size for the Regulatory Authorities.
- The data displays for all TFLs will have a minimum blank 1-inch margin on all 4 sides.
- Headers and footers for figures will be in Courier New font, size 8 which is the smallest acceptable point size for the Regulatory Authorities.
- Legends will be used for all figures with more than 1 variable, group, or item displayed.
- TFLs will be in black and white (no colour).
- Specialized text styles, such as bolding, italics, borders, shading, and superscripted and subscripted text, will not be used in the TFLs, unless otherwise specified. On some occasions, superscripts 1, 2, or 3 may be used (see below).
- Only standard keyboard characters will be used in the TFLs. Special characters, such as non-printable control characters, printer-specific, or font-specific characters, will not be used. Hexadecimal-derived characters will be used, where possible, if they are appropriate to help display math symbols (e.g., μ). Certain subscripts and superscripts (e.g., cm^2 , C_{max}) may be employed on a case-by-case basis.
- Mixed case will be used for all titles, footnotes, column headers, and programmer-supplied formats, as appropriate.

Headers

- All output should have the following header at the top left of each page:

Zambon Protocol Z7224L01 [REDACTED] study number [REDACTED])

- All output should specify the Draft/Final Run status at the top centre of each page.
- All output should have Page n of N at the top right corner of each page. TFLs are internally paginated in relation to the total length (i.e., the page number should appear sequentially as page n of N, where N is the total number of pages in the table).

CONFIDENTIAL

Sponsor:	Zambon S.p.A.	Protocol Number:	Z7224L01
----------	---------------	------------------	----------

- The date output was generated should appear along with the program name as a footer on each page.

Display Titles

- Each output is identified by the designation and a numeral. (i.e., Table 14.1.1). ICH E3 numbering is strongly recommended. A decimal system (x.y and x.y.z) is used to identify TFLs with related contents. All titles will be centre-aligned. The analysis population will be identified on the line immediately following the title. The output number and title will be single-line spaced. A solid line spanning the margins will separate the display titles from the column headers. There will be one blank line between the last title and the solid line.

Table x.y.z
 First Line of Title
 Second Line of Title if Needed
 (mITT Population)

In a listing, in the case that a subject's record has been continued to the next page, an appropriate identification (e.g., the subject ID number) must be presented at the beginning of that page.

